### Appendix 3. Endpoint Derivations

#### Eczema Area and Severity Index (EASI)

The EASI quantifies the severity of a subject’s atopic dermatitis based on both severity of lesion clinical signs and the percent of BSA affected. EASI is a composite scoring by the atopic dermatitis clinical evaluator of the degree of erythema, induration/papulation, excoriation, and lichenification (each scored separately) for each of four body regions, with adjustment for the percent of BSA involved for each body region and for the proportion of the body region to the whole body.

**Lesion Severity by Clinical Signs:** The basic characteristics of atopic dermatitis lesions-erythema, induration/papulation, excoriation, and lichenification-provide a means for assessing the severity of lesions. Assessment of these four main clinical signs is performed separately for four body regions: head and neck, upper limbs, trunk (including axillae and groin) and lower limbs (including buttocks). Average erythema, induration/papulation, excoriation, and lichenification are scored for each body region according to a 4-point scale: 0=absent; 1=mild; 2=moderate; 3=severe. Morphologic descriptors for each clinical sign severity score are shown in the table below.

#### Clinical Sign Severity Scoring Criteria for the EASI

| Score                     |          | Description*   |
|---------------------------|----------|--|
| Erythema (E)              |          |  |
| 0                         | Absent   | None; may have residual discoloration (post-inflammatory hyperpigmentation and/or hypopigmentation). |
| 1                         | Mild     | Light pink to light red  |
| 2                         | Moderate | Red  |
| 3                         | Severe   | Deep, dark red   |
| Induration/Papulation (I) |          |  |
| 0                         | Absent   | None   |
| 1                         | Mild     | Barely palpable to slight, but definite hard thickened skin and/or papules                           |
| 2                         | Moderate | Easily palpable moderate hard thickened skin and/or papules  |
| 3                         | Severe   | Severe hard thickened skin and/or papules  |
| Excoriation (Ex)          |          |  |
| 0                         | Absent   | None   |
| 1                         | Mild     | Slight, but definite linear or picked scratch marks or penetrating surface injury                    |
| 2                         | Moderate | Moderate linear or picked scratch marks or penetrating surface injury                                |
| 3                         | Severe   | Severe linear or picked scratch marks or penetrating surface injury                                  |
| Lichenification (L)       |          |  |

|   |          |  |
|---|----------|--|
| 0 | Absent   | None   |
| 1 | Mild     | Barely perceptible to slight, but definite thickened skin, fine skin markings, and lichenoid scale |
| 2 | Moderate | Moderate thickened skin, coarse skin markings, and coarse lichenoid scale                          |
| 3 | Severe   | Severe thickened skin with very coarse skin markings and lichenoid scale                           |

\* The EASI will exclude scalp, palms, and soles from the assessment/scoring.

**%BSA with Atopic Dermatitis:** The number of handprints of skin afflicted with atopic dermatitis in a body region can be used to determine the extent (%) to which a body region is involved with atopic dermatitis (see table below). When measuring, the handprint unit refers to the size of each individual subject’s hand with fingers in a closed position.

**Handprint Determination of %BSA**

| Body Region                                  | Total Number of Handprints in Body Region* | Surface Area of Body Region Equivalent of One Handprint* |
|--|--|--|
| Head and Neck                                | 10   | 10%  |
| Upper Limbs                                  | 20   | 5%   |
| Trunk (including axillae and groin/genitals) | 30   | 3.33%  |
| Lower Limbs (including buttocks)             | 40   | 2.5%   |

Handprint refers to the hand size of each individual subject.

\* The number of handprints will be for the entire body region; these values will not be adjusted for exclusion of scalp, palms, and soles from the BSA assessment.

**EASI Area Score Criteria**

| Percent BSA with Atopic Dermatitis in a Body Region | Area Score |
|---|------------|
| 0%  | 0          |
| >0 - <10%   | 1          |
| 10 - <30%   | 2          |
| 30 - <50%   | 3          |
| 50 - <70%   | 4          |
| 70 - <90%   | 5          |
| 90 - 100%   | 6          |

**Body Region Weighting:** Each body region is weighted according to its approximate percentage of the whole body (see table below).

**EASI Body Region Weighting**

| Body Region                           | Body Region Weighting |
|--|------------------------------|
| Head and Neck                                | 0.1                          |
| Upper Limbs                                  | 0.2                          |
| Trunk (including axillae and groin/genitals) | 0.3                          |
| Lower Limbs (including buttocks)             | 0.4                          |

\* No adjustment for body regions excluded for assessment.

In each body region, the sum of the Clinical Signs Severity Scores for erythema, induration/papulation, excoriation, and lichenification is multiplied by the Area Score and by the Body Region Weighting to provide a body region value, which is then summed across all four body regions resulting in an EASI score as described in Equation below.

$$EASI = 0.1Ah(Eh+Ih+Exh+Lh) + 0.2Au(Eu+Iu+ExU+Lu) + 0.3At(Et+It+Ext+Lt) + 0.4Al(El+Il+Exl+Ll)$$

A = Area Score; E = erythema; I = induration/papulation; Ex = excoriation; L = lichenification; h = head and neck; u = upper limbs; t = trunk; l = lower limbs.

The EASI score can vary in increments of 0.1 and range from 0.0 to 72.0, with higher scores representing greater severity of atopic dermatitis.

**Investigator’s Global Assessment (IGA)**

The Investigator’s Global Assessment of atopic dermatitis is scored on a 5-point scale (0-4), reflecting a global consideration of the erythema, induration and scaling. The clinical evaluator of atopic dermatitis will perform an assessment of the overall severity of atopic dermatitis and assign an IGA score and category as described in the table below. The assessment will be a static evaluation without regard to the score at a previous visit.

**IGA Score**

| Score | Category     | Description*   |
|-------|--------------|--|
| 0     | Clear        | Atopic dermatitis is cleared, except for any residual discoloration (post-inflammatory hyperpigmentation and/or hypopigmentation).   |
| 1     | Almost Clear | Overall, the atopic dermatitis is not entirely cleared and remaining lesions are light pink (not including post inflammatory hyperpigmentation) and/or; have barely palpable hard thickened skin and/or papules and/or; have barely perceptible lichenification; excoriation and oozing/crusting are absent.                               |
| 2     | Mild         | Overall, the atopic dermatitis consists of lesions that are light red; with slight, but definite hard thickened skin and/or papules; with slight, but definite linear or picked scratch marks or penetrating surface injury; with slight, but definite thickened skin, fine skin markings, and lichenoid scale; oozing/crusting is absent. |
| 3     | Moderate     | Overall, the atopic dermatitis consists of lesions that are red; with easily palpable moderate hard thickened skin and/or papules; with moderate linear or picked scratch marks or penetrating surface injury; with moderate thickened skin, coarse skin markings, and coarse lichenoid scale; with slight oozing/crusting.                |
| 4     | Severe       | Overall, the atopic dermatitis consists of lesions that are deep, dark red; with severe hard thickened skin and/or papules; with severe linear or picked scratch marks or penetrating surface injury; with severe thickened skin with very coarse skin markings and lichenoid scale; with moderate to severe oozing/crusting.              |

\* The IGA will exclude scalp, palms, and soles from the assessment/scoring.

[figure not shown]
**Peak Pruritus Numerical Severity Scale (PP-NRS)**

On a scale of 0 to 10, with 0 being “no itch” and 10 being “worst itch imaginable”, how would you rate your itch at the worst moment during the previous 24 hours?

|                          |                          |                          |                          |                          |                          |                          |                          |                          |                          |                             |
|--------------------------|--------------------------|--------------------------|--------------------------|--------------------------|--------------------------|--------------------------|--------------------------|--------------------------|--------------------------|-----------------------------|
|  |  |  |  |  |  |  |  |  |  |     |
| 0                        | 1                        | 2                        | 3                        | 4                        | 5                        | 6                        | 7                        | 8                        | 9                        | 10                          |
| No
itch               |                          |                          |                          |                          |                          |                          |                          |                          |                          | Worst
itch
imaginable |

CCI

[Redacted]

PFIZER CONFIDENTIAL

Page 41

[Redacted]

### Psoriasis Area Severity Index (PASI)

The Psoriasis Area and Severity Index quantifies the severity of a subject's psoriasis based on both lesion severity and the percentage of body surface area affected. Lesion severity: the basic characteristics of psoriatic lesions - erythema, induration and scaling - provide a means for assessing the severity of lesions. Assessment of these three main signs is performed separately for four areas of the body: head, upper limbs, trunk, and lower limbs. Average erythema, induration and scaling are rated for each body area according to a 5-point scale: 0, no involvement; 1, slight; 2, moderate; 3, marked; 4, very marked.

Body surface area (BSA) involvement: the extent (%) to which each of the four areas of the body is affected by psoriasis is assigned a numerical score according to the following area scoring criteria: 0, no involvement; 1, >0 to 9%; 2, 10 to 29%; 3, 30 to 49%; 4, 50 to 69%; 5, 70 to 89%; 6, 90 to 100%. Details see Table 5 of the protocol.

### Derivation of PASI score

In each area, the sum of the severity rating scores for erythema, induration and scaling is multiplied by the score representing the percentage of this area involved by psoriasis, multiplied by a weighting factor (head 0.1; upper limbs 0.2; trunk 0.3; lower limbs 0.4). The sum of the numbers obtained for each of the four body areas is the PASI.

$$\text{PASI} = 0.1A_h(E_h + I_h + S_h) + 0.2A_u(E_u + I_u + S_u) + 0.3A_t(E_t + I_t + S_t) + 0.4A_l(E_l + I_l + S_l)$$

where A = area of involvement score; E = erythema; I = induration; S = scaling; h = head;  
u = upper limbs; t = trunk; l = lower limbs

The PASI score can vary in increments of 0.1 units from 0.0 to 72.0, with higher scores representing increasing severity of psoriasis.

### PASI C/75/CCI response

At least C/75/CCI % reduction in PASI relative to baseline PASI Score.

### Body Surface Area (BSA)

Assessment of body surface area involved in psoriasis is performed separately for four areas of the body: head, upper limbs, trunk, and lower limbs. The percentage surface area affected by psoriasis is estimated by means of the "handprint method", where the full hand of the subject (ie, the subject's flat hand, thumb and fingers) represents approximately 1% of the total BSA and a set percentage of each of the four areas of the body:

- 1 handprint corresponds to approximately 10% of the head/neck;
- 1 handprint corresponds to approximately 5% of the arm/upper limbs;
- 1 handprint corresponds to approximately 3.3% of the trunk;
- 1 handprint corresponds to approximately 2.5% of the lower limbs.

The extent (%) to which each of the four areas of the body is affected is captured on the CRF (to 2 decimal places, as necessary). A weighting factor is applied to each of the four areas in calculation of the total body surface area affected: head x0.1; upper limbs x0.2; trunk x0.3; lower limbs x0.4, as the four areas correspond to approximately 10%, 20%, 30% and 40% of the total BSA, respectively. The sum of the weighted percent involvement obtained for each of the four body areas is the overall psoriatic BSA.

**Handprint Determination of %BSA**

| Body Region                           | Total Number of Handprints in Body Region* | Surface Area of Body Region Equivalent of One Handprint* |
|--|---|---|
| Head and Neck                                | 10  | 10%   |
| Upper Limbs                                  | 20  | 5%  |
| Trunk (including axillae and groin/genitals) | 30  | 3.33%   |
| Lower Limbs (including buttocks)             | 40  | 2.5%  |

Handprint refers to the hand size of each individual subject.

\* The number of handprints will be for the entire body region; these values will not be adjusted for exclusion of scalp, palms, and soles from the BSA assessment.

**Physician Global Assessment (PGA)**

The Physician Global Assessment of psoriasis is scored on a 5-point scale, reflecting a global consideration of the erythema, induration and scaling across all psoriatic lesions. Average erythema, induration and scaling are rated separately over the whole body according to a 5-point severity scale, scored from 0 to 4, with appropriate morphologic descriptors. The severity rating scores are summed and the average taken - the total average is rounded to the nearest whole number score to determine the PGA. The 5-point scale for PGA is: 0, "clear"; 1, "almost clear"; 2, "mild"; 3, "moderate"; 4 "severe".

CCI

CCI

CCI

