4. STUDY DESIGN

4.1. Overall Design

This is a phase 2a, randomized, double blind, vehicle controlled, parallel group, multicenter study on the efficacy, safety, tolerability and PK of PF-07038124 0.01% QD versus vehicle control in the treatment of adult participants with mild to moderate AD or mild to moderate plaque psoriasis. In this study the efficacy of PF-07038124 ointment versus vehicle will be assessed in two different indications – there is a separate vehicle control group for each indication.

A total of approximately 88 participants with AD or psoriasis will be randomly assigned to study intervention in this basket trial design.

For AD, a maximum of approximately 56 participants will be randomly assigned to study intervention such that approximately 42 evaluable participants complete the study. Assuming a 25% drop out rate, approximately 28 participants will be randomized to either PF-07038124 or vehicle control to achieve approximately 21 completers in each group. Randomization will be stratified by baseline disease severity (mild [Investigator's Global Assessment or IGA = 2] vs. moderate [IGA = 3]). Up to 25% of AD participants will have an IGA score of 2 at baseline.

For psoriasis, a maximum of approximately 32 participants will be randomly assigned to study intervention such that approximately 24 evaluable participants complete the study. Assuming a 25% drop out rate, approximately 16 participants will be randomized to PF-07038124 or vehicle control to achieve 12 completers in each group. Randomization will be stratified by baseline disease severity (mild [Physician Global Assessment or PGA = 2] vs. moderate [PGA = 3]). Up to 25% of participants will have a PGA score of 2 at baseline.

The total duration of study participation will be approximately 17 weeks, including a screening period of up to 6 weeks, a double-blind, placebo-controlled treatment period of 6 weeks, and a safety follow-up period of 4-5 weeks from last dose of study drug to last study visit. The study intervention arms and duration for AD and psoriasis participants are the same (See [Section 1.1](#) for detailed Study Intervention Groups and [Section 1.2](#) for Study Schema).

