5.1.2.2. Psoriasis Specific Inclusion Criteria

1. Participants with a diagnosis of plaque psoriasis (psoriasis vulgaris) for at least 6 months prior to Day 1.
2. Participants with a Physician Global Assessment (PGA) score of 2 (mild), or 3 (moderate) at Screening and Day 1. Note: Refer to [Section 8.1.4.2](#) for the assessment of 5-point PGA.
3. Having plaque psoriasis covering 5% to 15% (inclusive) of BSA (excluding the scalp) at both the Screening and Day 1/Randomization. Note: Refer to [Section 8.1.4.3](#) for detailed methods of calculating treatable BSA.

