8.1.4.2. Physician Global Assessment

The Physician Global Assessment (PGA) of psoriasis is scored on a descriptive 5-point scale.¹² The 5-point scale for PGA is: 0, “clear”; 1, “almost clear”; 2, “mild”; 3, “moderate”; 4 “severe” (Table 14). The assessment will be a static evaluation without regard to the score at a previous visit.

Table 14. Physician Global Assessment (PGA) Score

Physician’s Global Assessment		Description
0	Clear	No signs of psoriasis; post-inflammatory hyperpigmentation may be present
1	Almost Clear	No thickening; normal to pink coloration; no to minimal focal scaling
2	Mild	Just detectable to mild thickening; pink to light red coloration; predominantly fine scaling
3	Moderate	Clearly distinguishable to moderate thickening; dull to bright red, clearly distinguishable to moderate thickening; moderate scaling
4	Severe	Severe thickening with hard edges; bright to deep dark red coloration; severe/coarse scaling covering almost all or all lesions

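### The SAP derives PGA by averaging and rounding three sign ratings, while the protocol has the rater assign one descriptive grade; the two rules can disagree on responder status for the psoriasis key secondary endpoint

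*SAP*

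**What the plan says.** **Protocol.** Section 8.1.4.2 states: "The Physician Global Assessment (PGA) of psoriasis is scored on a descriptive 5-point scale". The rater chooses one static grade from the row descriptions in Table 14. Grade 0 reads "No signs of psoriasis; post-inflammatory hyperpigmentation may be present", grade 1 reads "No thickening; normal to pink coloration; no to minimal focal scaling", and grade 3 begins "Clearly distinguishable to moderate thickening; dull to bright red". Thickening that is only just detectable belongs to grade 2. Nothing is averaged or rounded. In the protocol, separate ratings of the three signs belong to PASI, by body region (8.1.4.1).

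The same PGA is an entry criterion in 5.1.2.2: "Participants with a Physician Global Assessment (PGA) score of 2 (mild), or 3 (moderate) at Screening and Day 1". It also defines the randomization strata in 4.1, where the mild stratum is capped: "Up to 25% of participants will have a PGA score of 2 at baseline".

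**SAP.** The PGA paragraph of Appendix 3 says: "Average erythema, induration and scaling are rated separately over the whole body", each from 0 to 4. The three scores are then averaged, and "the total average is rounded to the nearest whole number score to determine the PGA". Table 14 is not reproduced in the visible text. For IGA, the AD counterpart, the same appendix keeps the protocol's single grade without averaging.

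**Use.** A PGA of 0 or 1 with a gain of at least 2 grades at Week 6 is the psoriasis key secondary endpoint (protocol 9.2.2, SAP 5.1). SAP 3.2 also lists it at the other visits.

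**The concern.** The documents give two algorithms for one variable. A rule that averages three signs can offset a worse sign against two better ones. A descriptive grade such as almost clear, which rules out thickening altogether, does not allow that. The rules can therefore part at the response threshold at Week 6.

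They can also part at baseline. The gain of 2 grades would then be measured from a value that differs from the one used to admit and stratify the participant. If both a grade and component scores exist at analysis, the choice between them is open after the data are seen. In arms of 16, a few such cases would be visible in the response rates.

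**Working it through.** **The plan's own figure.** Protocol 9.2.2 assumes response rates of 20% and 65%, two-sided alpha 0.05 and 12 evaluable per arm, and states 61.9% power. With the pooled-variance normal approximation the mean rate is 0.425, and

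z = (0.45·√12 − 1.96·√(2·0.425·0.575)) / √(0.20·0.80 + 0.65·0.35) = (1.559 − 1.370) / 0.622 = 0.303,

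which gives a power of 0.619. The figure reproduces. It does not depend on how PGA is derived, so it is not in question.

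**The two rules on the same profile.** Write a profile as (erythema, induration, scaling). The SAP rule is PGA = round((E + I + S)/3). A responder needs a final grade of 0 or 1 and a gain of at least 2, so baseline 3 needs grade 0 or 1, and baseline 2 needs grade 0. The examples assume that each component score is anchored to the Table 14 row of the same number.

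| Example | Profile | Mean | SAP grade | Table 14 reading | Consequence |
|---|---|---|---|---|---|
| a | Week 6 (1,2,1), baseline 3 | 4/3 = 1.33 | 1 | Thickening excludes grade 1; rater likely records 2 | SAP responder; non-responder at recorded grade 2 |
| b | Week 6 (1,0,0), baseline 2 | 1/3 = 0.33 | 0 | Grade 0 allows no signs; grade 1 if colour is visibly pink | SAP responder; non-responder at recorded grade 1 |
| c | Baseline (2,3,2), later grade 1 under both rules | 7/3 = 2.33 | 2 at baseline | Thickening is that of moderate; rater may record 3 | Gain 2 − 1 = 1, SAP non-responder; gain 3 − 1 = 2, responder at recorded grade 3 |

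**Are these contrived profiles?** In all three, the components lie within one grade of each other. Of the 5³ = 125 possible profiles, 29 have that property (5 uniform, plus 4 adjacent pairs × 6). Within those 29, (1,2,1) is the only one that rounds to 1 with induration 2 or more, and (2,3,2) the only one that rounds to 2 with induration 3 or more. (1,0,0) and (0,0,1) round to 0 with redness or scale scored. These counts locate the examples; they are not frequencies.

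**Does the result hang on the anchoring?** Use the PASI descriptors of protocol Table 10 instead, where induration 1 already means slight elevation. Then (1,1,1) averages 1.0, so the SAP grade is 1, while Table 14 places just-detectable thickening at grade 2. Which profiles disagree changes with the anchoring, but disagreement occurs under both.

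**Who could be affected.** Example b concerns baseline PGA 2: up to 25% × 32 = 8 participants. Examples a and c concern the remaining 24 or more.

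**Step size.** The mITT analysis counts missing data as non-response, so the denominator is about 16 per arm. One participant is 100/16 = 6.25 points. If 0 to 2 participants in one arm were reclassified (an assumption, not an estimate), the shift would be 0 to 12.5 points.

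**The case against.** The strongest reply is that the SAP rule may never run. The psoriasis schedule of activities lists a single PGA item and no whole-body component ratings. If only the grade is recorded, the recorded grade will be analysed and nobody is reclassified. If sites instead derive PGA from components throughout, one value feeds eligibility, stratum and analysis, and the baseline mismatch disappears. Reclassification requires both to be collected, with the SAP derivation overriding the grade. This limits any claim about a numerical effect, and none is made. It does not rescue the paragraph: it is either impossible to execute or a departure from the protocol's scoring.

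The examples rest on an assumed mapping, since the SAP's component descriptors are not visible and blacked-out text follows the paragraph. Example b is the weakest, because the colour and scaling in row 1 overlap those of row 0. Table 14 also has no explicit rule for mixed profiles, so the rater's grade of 2 in example a is a likely reading and not a stated one.

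The SAP is allowed to modify the protocol, and a secondary endpoint would not need an amendment. But no visible entry in SAP Table 1 declares a PGA change. The neighbouring PASI text points to protocol Table 5, an EASI table, for area scoring that is in Table 12. That suggests, without proving, that text was carried over from elsewhere.

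Two smaller objections largely stand. The stratum has no analytic consequence, because neither the Chan and Zhang analysis nor the ANCOVA uses it. The reference to the whole body may simply contrast with PASI's regional scoring, and the protocol already limits all psoriasis efficacy assessments to treated areas with exclusions. Both are alignment points only.

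**Conclusion.** The concern holds. The SAP and the protocol define PGA by different rules, and those rules can give different responder status and different baselines. The frequency and net direction are unknown: examples a and b add a responder under the SAP rule, while example c can remove one. The 6.25 points per participant is a step size, not an expected bias. The inconsistency itself is certain. The specific examples rest on the assumed anchoring, and any actual reclassification requires that component scores be collected, which is not visible.

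The effect is confined to the PGA endpoints. SAP 5.1 rests inference on EASI and PASI, so the primary analyses stand. This should be corrected, but it does not threaten the trial's main conclusion.

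**What to change.** Replace the PGA paragraph in SAP Appendix 3 with the protocol definition: PGA is the single grade the rater records from protocol Table 14, without averaging or rounding, on treated areas excluding scalp, palms, soles and nails. State that this recorded grade serves as baseline, matches the grade used for the stratum, and is used at every post-baseline visit. Check the CRF at the same time; if component ratings are collected, say that they are not used to derive PGA. Do this before unblinding. The cost is one SAP paragraph, and no sample-size or power figure changes.
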